## 3.11 Exposure

.

Exposure	Plitidepsin (N=XX	2.5mg (X)	Plitidepsin (N=XX	1.5mg (X)		Control Arm (N=XXX)	
Statistic	Dexamethasone	Plitidepsin	Dexamethasone	Plitidepsin	Dexamethasone	Remdesivir	Favipiravir
Number of Patients with at least one Infusion/Dose Administered, n	XXX	XXX	XXX	xxx	XXX	XXX	xxx
Duration of Exposure (days) [a]							
n	XXX	XXX	XXX	XXX	XXX	XXX	XXX
Mean (SD)	xx.x (xx.xx)	xx.x (xx.xx)	xx.x (xx.xx)	xx.x (xx.xx)	xx.x (xx.xx)	xx.x (xx.xx)	xx.x (xx.xx)
Median	XX.X	XX.X	XX.X	XX.X	XX.X	XX.X	XX.X
Q1, Q3	xx.x, xx.x	xx.x, xx.x	XX.X, XX.X	xx.x, xx.x	xx.x, xx.x	xx.x, xx.x	xx.x, xx.x
Min, Max	XX, XX	xx, xx	XX, XX	xx, xx	xx, xx	xx, xx	XX, XX
Days with Doses Administered							
n	XXX	XXX	XXX	XXX	XXX	XXX	XXX
Mean (SD)	xx.x (xx.xx)	xx.x (xx.xx)	xx.x (xx.xx)	xx.x (xx.xx)	xx.x (xx.xx)	xx.x (xx.xx)	xx.x (xx.xx)
Median	XX.X	XX.X	XX.X	XX.X	XX.X	XX.X	XX.X
Q1, Q3	XX.X, XX.X	XX.X, XX.X	XX.X, XX.X	XX.X, XX.X	XX.X, XX.X	XX.X, XX.X	XX.X, XX.X
Min, Max	XX, XX	XX, XX	XX, XX	xx, xx	xx, xx	xx, xx	XX, XX
Days with Doses Administered, n (%)							
1 day	xxx (xxx.x)	xxx (xxx.x)	xxx (xxx.x)	xxx (xxx.x)	xxx (xxx.x)	xxx (xxx.x)	xxx (xxx.x)
2 days	xxx (xxx.x)	xxx (xxx.x)	xxx (xxx.x)	xxx (xxx.x)	xxx (xxx.x)	xxx (xxx.x)	xxx (xxx.x)
3 days	xxx (xxx.x)	xxx (xxx.x)	xxx (xxx.x)	xxx (xxx.x)	xxx (xxx.x)	xxx (xxx.x)	xxx (xxx.x)
4 days	xxx (xxx.x)	NA	xxx (xxx.x)	NA	xxx (xxx.x)	xxx (xxx.x)	xxx (xxx.x)
5 days	xxx (xxx.x)	NA	xxx (xxx.x)	NA	xxx (xxx.x)	xxx (xxx.x)	xxx (xxx.x)
6 days	xxx (xxx.x)	NA	xxx (xxx.x)	NA	xxx (xxx.x)	NA	NA
7 days	xxx (xxx.x)	NA	xxx (xxx.x)	NA	xxx (xxx.x)	NA	NA
8 days	xxx (xxx.x)	NA	xxx (xxx.x)	NA	xxx (xxx.x)	NA	NA
9 days	xxx (xxx.x)	NA	xxx (xxx.x)	NA	xxx (xxx.x)	NA	NA
10 days	xxx (xxx.x)	NA	xxx (xxx.x)	NA	xxx (xxx.x)	NA	NA
>10 days	xxx (xxx.x)	NA	xxx (xxx.x)	NA	xxx (xxx.x)	NA	NA

### Table 14.3.1.1 Summary of Exposure (As Treated Population)

N = number of patients in analysis set; n = number of patients with data available; % = percentages are calculated based on the number of patients with at least one infusion/dose administered as the denominator.

SD = Standard deviation; Q1 = 25th percentile; Q3 = 75th percentile; Min = Minimum; Max = Maximum; NA= Not Applicable.

[a] Duration is defined as (last dose date - first dose date + 1).

Reference: Listing 16.2.5.1 and 16.2.5.2

- Table template TLB004B.
- The displayed xxx do not reflect actual decimal precision. Please follow Section 2.11 for rounding rules.
  The ">10 infusions/doses" category should only be presented if there are any cases in any treatment group.

Exposure	Plitidepsin (N=XX	1 2.5mg (X)	Plitidepsin (N=XX	1.5mg (X)		Control Arm (N=XXX)	
Statistic	Dexamethasone	Plitidepsin	Dexamethasone	Plitidepsin	Dexamethasone	Remdesivir	Favipiravir
Days where Total Amount was Administered							
n M (CD)	XXX	XXX	XXX	XXX	XXX	XXX	XXX
Mean (SD)	xx.x (xx.xx)	xx.x (xx.xx)	xx.x (xx.xx)	xx.x (xx.xx)	xx.x (xx.xx)	xx.x (xx.xx)	xx.x (xx.xx)
Median	XX.X	XX.X	XX.X	XX.X	XX.X	XX.X	XX.X
Q1, Q3	XX.X, XX.X	xx.x, xx.x	XX.X, XX.X	xx.x, xx.x	XX.X, XX.X	XX.X, XX.X	XX.X, XX.X
Min, Max	xx, xx	xx, xx	xx, xx	xx, xx	xx, xx	xx, xx	XX, XX
Days where Total Amount was Administered, n (%)							
0 day	xxx (xxx.x)	xxx (xxx.x)	xxx (xxx.x)	xxx (xxx.x)	xxx (xxx.x)	xxx (xxx.x)	xxx (xxx.x)
1 day	xxx (xxx.x)	xxx (xxx.x)	xxx (xxx.x)	xxx (xxx.x)	xxx (xxx.x)	xxx (xxx.x)	xxx (xxx.x)
2 days	xxx (xxx.x)	xxx (xxx.x)	xxx (xxx.x)	xxx (xxx.x)	xxx (xxx.x)	xxx (xxx.x)	xxx (xxx.x)
3 days	xxx (xxx.x)	xxx (xxx.x)	xxx (xxx.x)	xxx (xxx.x)	xxx (xxx.x)	xxx (xxx.x)	xxx (xxx.x)
4 days	xxx (xxx.x)	NA	xxx (xxx.x)	NA	xxx (xxx.x)	xxx (xxx.x)	xxx (xxx.x)
5 days	xxx (xxx.x)	NA	xxx (xxx.x)	NA	xxx (xxx.x)	xxx (xxx.x)	xxx (xxx.x)
6 days	xxx (xxx.x)	NA	xxx (xxx.x)	NA	xxx (xxx.x)	NA	NA
7 days	xxx (xxx.x)	NA	xxx (xxx.x)	NA	xxx (xxx.x)	NA	NA
8 days	xxx (xxx.x)	NA	xxx (xxx.x)	NA	xxx (xxx.x)	NA	NA
9 days	xxx (xxx.x)	NA	xxx (xxx.x)	NA	xxx (xxx.x)	NA	NA
10 days	xxx (xxx.x)	NA	xxx (xxx.x)	NA	xxx (xxx.x)	NA	NA
>10 days	xxx (xxx.x)	NA	xxx (xxx.x)	NA	xxx (xxx.x)	NA	NA

### Table 14.3.1.1 Summary of Exposure (As Treated population)

N = number of patients in analysis set; n = number of patients with data available; % = percentages are calculated based on the number of patients with at least one infusion/dose administered as the denominator.

SD = Standard deviation; Q1 = 25th percentile; Q3 = 75th percentile; Min = Minimum; Max = Maximum; NA= Not Applicable.

[a] Duration is defined as (last dose date - first dose date + 1).

Reference: Listing 16.2.5.1 and 16.2.5.2

- Table template TLB004B.
- The displayed xxx do not reflect actual decimal precision. Please follow Section 2.11 for rounding rules.
- The ">10 infusions/doses" category should only be presented if there are any cases in any treatment group.

Exposure	Plitidepsin (N=XX	2.5mg (X)	Plitidepsin (N=XX	1.5mg (X)		Control Arm (N=XXX)	
Statistic	Dexamethasone	Plitidepsin	Dexamethasone	Plitidepsin	Dexamethasone	Remdesivir	Favipiravir
Days where Total Amount was NOT Administered							
n NA (SP)	XXX	XXX	XXX	XXX	XXX	XXX	XXX
Mean (SD)	xx.x (xx.xx)	xx.x (xx.xx)	xx.x (xx.xx)	xx.x (xx.xx)	xx.x (xx.xx)	xx.x (xx.xx)	xx.x (xx.xx)
Median	XX.X	XX.X	XX.X	XX.X	XX.X	XX.X	XX.X
Q1, Q3	XX.X, XX.X	XX.X, XX.X	XX.X, XX.X	XX.X, XX.X	xx.x, xx.x	XX.X, XX.X	XX.X, XX.X
Min, Max	xx, xx	xx, xx	xx, xx	xx, xx	xx, xx	xx, xx	xx, xx
Days where Total Amount was NOT Administered, n (%)							
0 day	xxx (xxx.x)	xxx (xxx.x)	xxx (xxx.x)	xxx (xxx.x)	xxx (xxx.x)	xxx (xxx.x)	xxx (xxx.x)
1 day	xxx (xxx.x)	xxx (xxx.x)	xxx (xxx.x)	xxx (xxx.x)	xxx (xxx.x)	xxx (xxx.x)	xxx (xxx.x)
2 days	xxx (xxx.x)	xxx (xxx.x)	xxx (xxx.x)	xxx (xxx.x)	xxx (xxx.x)	xxx (xxx.x)	xxx (xxx.x)
3 days	xxx (xxx.x)	xxx (xxx.x)	xxx (xxx.x)	xxx (xxx.x)	xxx (xxx.x)	xxx (xxx.x)	xxx (xxx.x)
4 days	xxx (xxx.x)	NA	xxx (xxx.x)	NA	xxx (xxx.x)	xxx (xxx.x)	xxx (xxx.x)
5 days	xxx (xxx.x)	NA	xxx (xxx.x)	NA	xxx (xxx.x)	xxx (xxx.x)	xxx (xxx.x)
6 days	xxx (xxx.x)	NA	xxx (xxx.x)	NA	xxx (xxx.x)	NA	NA
7 days	xxx (xxx.x)	NA	xxx (xxx.x)	NA	xxx (xxx.x)	NA	NA
8 days	xxx (xxx.x)	NA	xxx (xxx.x)	NA	xxx (xxx.x)	NA	NA
9 days	xxx (xxx.x)	NA	xxx (xxx.x)	NA	xxx (xxx.x)	NA	NA
10 days	xxx (xxx.x)	NA	xxx (xxx.x)	NA	xxx (xxx.x)	NA	NA
>10 days	xxx (xxx.x)	NA	xxx (xxx.x)	NA	xxx (xxx.x)	NA	NA

### Table 14.3.1.1 Summary of Exposure (As Treated population)

N = number of patients in analysis set; n = number of patients with data available; % = percentages are calculated based on the number of patients with at least one infusion/dose administered as the denominator.

SD = Standard deviation; Q1 = 25th percentile; Q3 = 75th percentile; Min = Minimum; Max = Maximum; NA= Not Applicable.

[a] Duration is defined as (last dose date - first dose date + 1).

Reference: Listing 16.2.5.1 and 16.2.5.2

- Table template TLB004B.
- The displayed xxx do not reflect actual decimal precision. Please follow Section 2.11 for rounding rules.
- The ">10 infusions/doses" category should only be presented if there are any cases in any treatment group.

Exposure	Plitidepsin (N=XX	2.5mg (X)	Plitidepsin (N=XX	1.5mg (X)		Control Arm (N=XXX)	
Statistic	Dexamethasone	Plitidepsin	Dexamethasone	Plitidepsin	Dexamethasone	Remdesivir	Favipiravir
Infusions Interrupted n Mean (SD) Median Q1, Q3 Min, Max	NA	XXX XX.X (XX.XX) XX.X XX.X, XX.X XX, XX	NA	XXX XX.X (XX.XX) XX.X XX.X, XX.X XX, XX	NA	NA	NA
Infusions Interrupted, n (%) 0 infusion 1 infusion 2 infusions 3 infusions	NA NA NA	xxx (xxx.x) xxx (xxx.x) xxx (xxx.x) xxx (xxx.x)	NA NA NA	xxx (xxx.x) xxx (xxx.x) xxx (xxx.x) xxx (xxx.x)	NA NA NA	NA NA NA	NA NA NA

### Table 14.3.1.1 Summary of Exposure (As Treated population)

N = number of patients in analysis set; n = number of patients with data available; % = percentages are calculated based on the number of patients with at least one infusion/dose administered as the denominator.

SD = Standard deviation; Q1 = 25th percentile; Q3 = 75th percentile; Min = Minimum; Max = Maximum; NA= Not Applicable. [a] Duration is defined as (last dose date - first dose date + 1).

Reference: Listing 16.2.5.1 and 16.2.5.2

- Table template TLB004B.
- The displayed xxx do not reflect actual decimal precision. Please follow Section 2.11 for rounding rules.

### 3.12 Adverse Events

Adverse Events Category	Plitidepsin 2.5mg	Plitidepsin 1.5mg	Plitidepsin Total	Control Arm
Auverse Events Type	n (%)	n (%)	n (%)	n (%)
Any IEAE	XXX (XXX.X)	xxx (xxx.x)	xxx (xxx.x)	XXX (XXX.X)
Grade I severity	xxx (xxx.x)	xxx (xxx.x)	xxx (xxx.x)	xxx (xxx.x)
Grade 2 severity	xxx (xxx.x)	xxx (xxx.x)	xxx (xxx.x)	xxx (xxx.x)
Grade 3 severity	XXX (XXX.X)	xxx (xxx.x)	xxx (xxx.x)	xxx (xxx.x)
Grade 4 severity	xxx (xxx.x)	xxx (xxx.x)	xxx (xxx.x)	xxx (xxx.x)
Grade 5 severity	xxx (xxx.x)	xxx (xxx.x)	xxx (xxx.x)	xxx (xxx.x)
$Grade \ge 3$	xxx (xxx.x)	xxx (xxx.x)	xxx (xxx.x)	xxx (xxx.x)
Leading to discontinuation of any study drug	xxx (xxx.x)	xxx (xxx.x)	xxx (xxx.x)	xxx (xxx.x)
Leading to death	xxx (xxx.x)	xxx (xxx.x)	xxx (xxx.x)	xxx (xxx.x)
Any treatment-related TEAE to any study drug [a]	xxx (xxx.x)	xxx (xxx.x)	xxx (xxx.x)	xxx (xxx.x)
$Grade \ge 3$	xxx (xxx.x)	xxx (xxx.x)	xxx (xxx.x)	xxx (xxx.x)
Leading to discontinuation of any study drug	xxx (xxx.x)	xxx (xxx.x)	xxx (xxx.x)	xxx (xxx.x)
Leading to death	xxx (xxx.x)	xxx (xxx.x)	xxx (xxx.x)	xxx (xxx.x)
Any treatment-related TEAE to plitidepsin [a]	xxx (xxx.x)	xxx (xxx.x)	xxx (xxx.x)	NA
$Grade \ge 3$	xxx (xxx.x)	xxx (xxx.x)	xxx (xxx.x)	NA
Leading to discontinuation of any study drug	xxx (xxx.x)	xxx (xxx.x)	xxx (xxx.x)	NA
Leading to death	xxx (xxx.x)	xxx (xxx.x)	xxx (xxx.x)	NA
Any treatment-related TEAE to dexamethasone [a]	xxx (xxx.x)	xxx (xxx.x)	xxx (xxx.x)	xxx (xxx.x)
$Grade \ge 3$	xxx (xxx.x)	xxx (xxx.x)	xxx (xxx.x)	xxx (xxx.x)
Leading to discontinuation of any study drug	xxx (xxx.x)	xxx (xxx.x)	xxx (xxx.x)	xxx (xxx.x)
Leading to death	xxx (xxx.x)	xxx (xxx.x)	xxx (xxx.x)	xxx (xxx.x)

### Table 14.3.1.2 Summary of Treatment-Emergent Adverse Events (TEAEs) (As Treated Population)

N = number of patients in analysis set; n = number of patients with data available; % = percentages are calculated based on N as the denominator.

TEAE = Treatment Emergent Adverse Event; NA= Not Applicable.

Note: TEAEs are events with start date on or after the date of first dose of any study drug or events with start date prior to the date of first dose of any study drug whose severity worsens on or after the date of first dose of any study drug. If the event started on the date of first dose of the first study drug administration however it is ticked as the event started prior to first study drug administration on Day 1 in the eCRF, it is not considered as a TEAE.

Adverse events were assigned severity grade using the Common Terminology Criteria for Adverse Events (CTCAE) Version 5.0.

[a] A treatment-related TEAE to any study drug, plitidepsin, dexamethasone or to the antiviral control arm, ie, the regulatory-approved antiviral for those patients randomised to the control arm (remdesivir or favipiravir), is an TEAE considered by the investigator as related to the corresponding study drug or with unknown/missing relationship to trial medication. MedDRA version & meddra.

Reference: Listing 16.2.7.1

- Table template TAE001.
- Assign the version of MedDRA Dictionary to & meddra. macro variable as XX.X and update the version of MedDRA Dictionary used for coding as needed.

Adverse Events Category Adverse Events Type	Plitidepsin 2.5mg (N=XXX)	Plitidepsin 1.5mg (N=XXX)	Plitidepsin Total (N=XXX)	Control Arm (N=XXX)
	n (%)	n (%)	n (%)	n (%)
Any treatment-related TEAE to the antiviral control arm [a]	NA	NA	NA	XXX (XXX X)
$Grade \ge 3$	NA	NA	NA	XXX (XXX.X)
Leading to discontinuation of any study drug	NA	NA	NA	xxx (xxx.x)
Leading to death	NA	NA	NA	xxx (xxx.x)
Any serious TEAE	xxx (xxx.x)	xxx (xxx.x)	xxx (xxx.x)	xxx (xxx.x)
$Grade \ge 3$	xxx (xxx.x)	xxx (xxx.x)	xxx (xxx.x)	xxx (xxx.x)
Leading to discontinuation of any study drug	xxx (xxx.x)	xxx (xxx.x)	xxx (xxx.x)	xxx (xxx.x)
Leading to death	xxx (xxx.x)	xxx (xxx.x)	xxx (xxx.x)	xxx (xxx.x)
Any serious treatment-related TEAE to any study drug [a]	xxx (xxx.x)	xxx (xxx.x)	xxx (xxx.x)	xxx (xxx.x)
$Grade \ge 3$	xxx (xxx.x)	xxx (xxx.x)	xxx (xxx.x)	xxx (xxx.x)
Any serious treatment-related TEAE to plitidepsin [a]	xxx (xxx.x)	xxx (xxx.x)	xxx (xxx.x)	NA
Any serious treatment-related TEAE to dexamethasone [a]	xxx (xxx.x)	xxx (xxx.x)	xxx (xxx.x)	xxx (xxx.x)
Any serious treatment-related TEAE to the antiviral control arm [a]	NA	NA	NA	xxx (xxx.x)
Any TEAE of special interest	xxx (xxx.x)	xxx (xxx.x)	xxx (xxx.x)	xxx (xxx.x)
$Grade \ge 3$	xxx (xxx.x)	xxx (xxx.x)	xxx (xxx.x)	xxx (xxx.x)
Leading to discontinuation of any study drug	xxx (xxx.x)	xxx (xxx.x)	xxx (xxx.x)	xxx (xxx.x)
Leading to death	xxx (xxx.x)	xxx (xxx.x)	xxx (xxx.x)	xxx (xxx.x)

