### 7.7.2 Adverse Events

All AEs recorded on the eCRF will be coded using the MedDRA dictionary (Version 24 [or a later version if updated during the study]) and classified as TEAEs as follows:

• TEAEs are events with start date on or after the date of first dose of any study drug or events with start date prior to the date of first dose of any study drug whose severity worsens on or after the date of first dose of any study drug. If the event started on the date of first dose of the first study drug administration however it is ticked as the event started prior to first study drug administration on Day 1 in the eCRF, it will not be considered as a TEAE.

All AE data will be listed by treatment group with TEAE status flagged in the listing. In addition, listings of grade  $\geq$ 3 AEs, SAEs, AEs leading to discontinuation of any study drug, AEs resulting in death and AEs of special interest will be produced.

The AEs of special interest will be based on MedDRA version 24.0. The terms that determine the AEs of special interest are:

- For Rhabdomyolysis, Musculoskeletal disorders and CPK increases:
  - Rhabdomyolysis/Myopathy (SMQ)
  - Additional PTs: Back pain, Pain in extremity, Arthralgia
- For Hypersensitivity reactions:
  - Hypersensitivity (SMQ)
- For Cardiac events:
  - Cardiomyopathy (SMQ)
  - Cardiac arrhythmias (SMQ)
  - Cardiac failure (SMQ)
  - Additional PTs: Acute myocardial infarction, Cardiovascular insufficiency, Coronary artery disease, Myocardial infarction, Angina pectoris, Aortic valve incompetence, Aortic valve sclerosis, Atrial thrombosis, Cardiac disorder, Degenerative aortic valve disease, Left ventricular hypertrophy, Mitral valve incompetence, Myocardial ischaemia, Pericardial effusion, Pericarditis, Subendocardial ischaemia, Tricuspid valve incompetence, Blood creatine phosphokinase MB increased, Blood pressure increased, Cardiac murmur, Electrocardiogram QRS complex abnormal, Electrocardiogram ST segment abnormal, Electrocardiogram ST segment depression, Electrocardiogram ST-T change, Electrocardiogram ST-T segment abnormal, Electrocardiogram T wave abnormal, Electrocardiogram T wave amplitude decreased, Electrocardiogram T wave inversion, Oxygen saturation decreased, Pulse abnormal, Respiratory rate,

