Troponin increased, Troponin I increased, Troponin T increased, Acute respiratory failure, Apnoea, Dyspnoea exertional, Hyperventilation, Hypoventilation, Hypoxia, Tachypnoea, Diastolic hypertension, Hypovolaemic shock, Systolic hypertension.

- For Hepatobiliary disorders and Transaminase elevations:
  - Hepatobiliary disorders (SOC)
  - Liver function analyses (HLT)

The final list of terms that determine the AEs of special interest will be described in the 'Analysis Set Specification' document to ensure the latest MedDRA version is used for the analyses.

Summary tables of TEAEs by treatment group and overall plitidepsin will be produced for the As Treated population.

Assessment of AE severity will be based on the NCI-CTCAE, version 5.0.

A treatment-related TEAE to plitidepsin, dexamethasone or to the antiviral control arm, ie, the regulatory-approved antiviral for those patients randomised to the control arm (remdesivir or favipiravir), is an TEAE considered by the investigator as related to the corresponding study drug or with unknown/missing relationship to trial medication.

An overview table will summarize the number and percentage of patients with at least one of the following TEAEs, where patients with more than one TEAE in a particular category are counted only once in that category:

- Any TEAE;
- Any TEAE by severity;
- Any TEAE grade  $\geq$ 3;
- Any TEAE leading to discontinuation of any study drug;
- Any TEAE leading to death;
- Any treatment-related TEAE to any study drug;
- Any treatment-related TEAE grade  $\geq$ 3 to any study drug;
- Any treatment-related TEAE to any study drug leading to discontinuation of any study drug;
- Any treatment-related TEAE to any study drug leading to death;
- Any treatment-related TEAE to plitidepsin;
- Any treatment-related TEAE grade  $\geq$ 3 to plitidepsin;
- Any treatment-related TEAE to plitidepsin leading to discontinuation of any study drug;
- Any treatment-related TEAE to plitidepsin leading to death;

- Any treatment-related TEAE to dexamethasone;
- Any treatment-related TEAE grade  $\geq$ 3 to dexamethasone;
- Any treatment-related TEAE to dexamethasone leading to discontinuation of any study drug;
- Any treatment-related TEAE to dexamethasone leading to death;
- Any treatment-related TEAE to antiviral control arm;
- Any treatment-related TEAE grade  $\geq$ 3 to antiviral control arm;
- Any treatment-related TEAE to antiviral control arm leading to discontinuation of any study drug;

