## **Appendix 4: Schedule of Assessments**

Procedure	Screening Day 0-1	Day 1	Day 2	Day 3	Day 4	Day 5	Day 6	Day 7	Day 8 (±1 day)	Day 9	Day 10	Day 15  (±1 day)	Day 31  (±3 days)
Informed consent 	X												
Selection criteria 	Х												
IWRS registration	Х	Х											Х
Medical history	X												
Vital signs 	X	Х	Х	Х	Х	Х	Х	Х	Х				Х
Demographics	X												
Charlson Comorbidity Index	Х												
Physical examination	X*	Х	Х	Х	Х				Х				Х
Electrocardiogram 	Х	Х		Х									Х
Haematology 	Х	Х	Х	Х	Х				Х				Х
Serum chemistry 	Х	Х	Х	Х	Х				Х				Х
Coagulation 		Х	Х	Х	Х				Х				Х
Serological test (IgG)		Х											Х
Immunology 		Х	Х	Х	Х				Х				Х
COVID-19 screen 	Х												
COVID-19 viral load 		Х							Х				
Chest imaging 		Х							Х				Х
Pregnancy test 	X												
Clinical status 	X	Х	Х	Х	Х	Х	Х	Х	Х			Х	Х
Functional status 	X								Х			Х	Х
Adverse events/TEAEs 	X	Х	Х	Х	Х	Х	Х	Х	Х	Х	Х	Х	Х
Concomitant medications 	X	Х	Х	Х	Х	Х	Х	Х	Х	Х	Х	Х	Х
Dexamethasone treatment 		Х	Х	Х	Х	Х	Х	Х	Х	Х	Х		
Plitidepsin treatment 		Х	Х	Х									
Remdesivir treatment 		Х	Х	Х	Х	Х							
Favipiravir treatment 		Х	Х	Х	Х	Х							
Premedication 		Х	Х	Х	Х	Х							

Abbreviations: ALT = alanine aminotransferase; AST = aspartate aminotransferase; BID = twice daily; BUN = blood urea nitrogen; COVID-19 = coronavirus disease 2019; CPK = creatine phosphokinase; CRP = C-reactive protein; ECG = electrocardiogram; GGT = gamma-glutamyl transferase; Ig = immunoglobulin; IL = interleukin; IV = intravenous; IWRS = interactive web response systems; LDH = lactate dehydrogenase; NIH = National Institute of Health; NT-pro-BNP = N-terminal pro B-type natriuretic peptide; PCR = polymerase chain reaction; PO = orally; qPCR = quantitative polymerase chain reaction; QTcF = QT interval corrected using Fridericia's formula; TEAE = treatment-emergent adverse event;  $TNF\alpha =$  tumour necrosis factor alpha.

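### A Day 1 adverse event that starts before the first dose and worsens after it is barred from TEAE status, although the same event starting a day earlier counts

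*SAP*

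**What the plan says.** SAP 7.7.2 gives two routes to TEAE status and one exclusion.

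- **Onset limb:** "TEAEs are events with start date on or after the date of first dose of any study drug".
- **Worsening limb:** "events with start date prior to the date of first dose of any study drug whose severity worsens on or after" that date.
- **Day 1 exclusion:** an event starting on the first-dose date is removed by this wording: "ticked as the event started prior to first study drug administration on Day 1 in the eCRF, it will not be considered as a TEAE".

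The same three-part definition is printed as a note under Tables 14.3.1.2, 14.3.1.3.1 to 14.3.1.3.5, 14.3.1.4.1 to 14.3.1.4.8, 14.3.2.3.1 to 14.3.2.3.4, 14.3.2.4.1 to 14.3.2.4.3, and 14.3.2.6.1 and 14.3.2.6.2, so it is the working rule for programming. In those notes the exclusion reads: "ticked as the event started prior to first study drug administration on Day 1 in the eCRF, it is not considered as a TEAE".

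On outputs, 7.7.2 states: "Summary tables of TEAEs by treatment group and overall plitidepsin will be produced for the As Treated population". It also states: "All AE data will be listed by treatment group with TEAE status flagged in the listing".

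**The concern.** The worsening limb commits the plan to a principle: an event already present before treatment becomes treatment-emergent if it gets worse once treatment has begun. The Day 1 exclusion departs from that principle for one group only, namely events that began on the dosing date but before dosing. Clinically, they are the same case as events that began the previous evening.

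The departure works in one direction: it can remove events from the TEAE tables but never add them. At stake are the TEAE-based safety counts: any TEAE, Grade 3 or higher, serious, special interest, leading to discontinuation and leading to death, together with the TEAE rows of the safety subgroup table (14.3.8.1).

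The situation can arise in this trial. Appendix 4 labels the screening column "Screening Day 0-1" and marks adverse events for collection from screening, so a pre-dose event can be recorded on the dosing date.

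**Working it through.** The SAP gives no figure to reproduce. The check is to apply the rule as written to every combination of onset and later worsening, and to compare it with a rule that extends the worsening limb to all pre-dose onsets.

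**Inputs (SAP 7.7.2):** the onset limb, the worsening limb and the Day 1 exclusion.

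**Rule as written:** TEAE if (start date ≥ first-dose date) or (start date < first-dose date and severity worsens), except that start date = first-dose date with the pre-dose tick gives not a TEAE.

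**Consistent rule:** call onset pre-dose if start date < first-dose date, or if start date = first-dose date with the tick. TEAE if onset is not pre-dose, or if severity worsens after dosing.

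| Onset | Worsens after dosing? | As written | Consistent rule |
|---|---|---|---|
| Day before first dose | No | Not TEAE | Not TEAE |
| Day before first dose | Yes | TEAE | TEAE |
| Day 1, ticked pre-dose | No | Not TEAE | Not TEAE |
| Day 1, ticked pre-dose | Yes | **Not TEAE** | **TEAE** |
| Day 1, not ticked | No | TEAE | TEAE |
| Day 1, not ticked | Yes | TEAE | TEAE |
| Day after first dose | No | TEAE | TEAE |
| Day after first dose | Yes | TEAE | TEAE |

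Exactly one of the eight rows differs. The second and fourth rows are both pre-dose onset with post-dose worsening, and the written rule separates them by calendar date alone. The third row shows that the tick-box keeps its purpose under the consistent rule: a Day 1 pre-dose event that does not worsen stays excluded.

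**Size.** The SAP gives neither the number of events ticked as pre-dose nor the share that worsen. Purely for scale, assume that 5% to 15% of patients have such an event and that 10% to 30% of those worsen. This gives 0.05 × 0.10 = 0.5% to 0.15 × 0.30 = 4.5% of patients. At an assumed 60 patients per arm, that is 60 × 0.005 = 0.3 to 60 × 0.045 = 2.7 patients. All of these inputs are assumptions, so the result is an illustration and not an estimate. It concerns worsening of any grade and says nothing about how many events would become Grade 3 or higher, serious or fatal.

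**The case against.** The strongest reply is that the gap is narrow and little safety information is lost.

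- **Visibility.** This stands. Section 7.7.2 lists all AEs, with further listings for Grade 3 or higher, serious, discontinuation, fatal and special-interest AEs, and none of these is limited to TEAEs. Deaths are summarised for the As Treated population without the flag (Table 14.3.2.1.2), and overall survival is analysed in the ITT population. Laboratory shift tables use the worst post-baseline grade, including unscheduled results (7.7.3). A reader might infer that every safety endpoint is distorted or that fatal events vanish from the report. The SAP does not support that: the loss is confined to TEAE-based summary counts.
- **Cause.** This also stands. A reader might infer that the excluded events were made worse by plitidepsin. The rule concerns timing only, is worded the same for all arms, and dexamethasone is study drug in every arm. No formal comparison of AEs between groups is planned either.
- **Data conventions.** This stands in part. If a worsening is entered as a new AE record with its own start date, the onset limb catches it and nothing is lost. The SAP states no such convention, however, and its worsening limb presupposes that one event is followed for change in severity.
- **Frequency.** This stands. A reader might take the screening label in Appendix 4 to mean that most pre-dose events fall on the dosing date. The SAP gives no distribution of screening-to-dose intervals.
- **Other rules lean towards inclusion.** Completely missing onset dates are set to the first-dose date (6.2), unknown or missing relationship counts as related, and Day 1 events without the tick are TEAEs. This shows no general tendency to under-count, but it does not repair the one case that is misclassified.

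**Conclusion.** The inconsistency is real and is visible from the wording alone. By the plan's own principle, an event that starts on Day 1 before dosing and worsens afterwards on the same AE record should be a TEAE, and the written rule says it is not. The effect is to lower TEAE-based counts, in any arm, by a number that the document does not allow anyone to derive. It may be small, or even zero.

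The conclusion assumes that worsening is held within the original AE record, as the worsening limb implies. It does not depend on any view of causality. The point is worth correcting because the misclassification runs in one direction and the repair is simple, not because a material distortion of the safety profile has been shown.

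**What to change.** In 7.7.2 and in every repeated TEAE note, end the last sentence with: *unless its severity worsens after the first study drug administration*. Apply the same condition in the TEAE derivation, and report by arm how many events it reclassifies. If the time of a same-day worsening is not recorded, state the convention used; the existing worsening limb already counts worsening dated on the first-dose date.

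The cost is one clause, one programming condition and a rerun of the TEAE tables. The severity information needed is what the worsening limb already requires, although the SAP does not describe how it is stored. TEAE counts may rise slightly. Because the database has been locked, the change would be made by addendum, a route the sponsor already uses for additional outputs. If a full rerun is not wanted, the count of reclassified events alone would show whether the issue matters.
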